Cover Letter

Study Title: Nighttime Postural Care: Caregiver Training Program and Outcome Measure Feasibility

Principal Investigator: [name]

Date of Document: October 31, 2017; Updated April 15, 2018

Date Document Uploaded to ClinicalTrials.gov: March 2, 2021

St. Catherine University IRB Amendment request Form

Submit your Amendment Request Form for your protocol through Mentor IRB at the bottom of the protocol page.

Investigators may request approval to make amendments in various aspects of a project. All changes must be approved by the IRB prior to implementation. Amendments include: changes in experimental design, insertion of new information, correction of errors in text, change in primary investigator, change in study duration, change in numbers of subjects, or number of locations (site). Upon completion of review, an approval notification will be sent to the primary investigator.

Primary Investigator:

[name] **Date:** 4/15/18

Title of Research Proposal:

Protocol ID:

1. What are the proposed changes?

Design change: Instead of one group of participants with pre/post questionnaires and demonstration of positioning a mock client (mock client is one of the research investigators), the participants will be randomized into treatment group (receives the sleep care positioning 2-hour online education program) and control group/lesser intervention (handout with series of web links) groups.

Participants will be blinded to the two group design, however the control group will be informed they were in the control group after completing the "lesser" intervention, the post-questionnaire and the demonstration of sleep positioning with mock client. On the same day the control group will be given the option to complete the same educational package as the treatment group (2-hour online sleep care positioning program).

Participants will complete a 12-20 item quiz after educational intervention. Since the online sleep care positioning training program is being delivered via Brightspace D2L. Statistics from the quizzes will be collected. The quiz is a new addition. This information will be compared along with the results from the questionnaires and demonstration of positioning a person in the sleep system to better understand if the training program leads to learning and competence thus revealing more about the feasibility of the training program for use in future clinical intervention study.

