Another change is that participants will only demonstrate the sleep positioning on a mock, rather than real client (i.e. person with CP, family member of research participant).

2. What is the rationale for proposed changes? The change results in a better research design. This randomized design will allow for a comparison group, allowing investigators to learn more about the merits of the educational (sleep care positioning training program) than would occur with only one pre/post group.

3. Do these changes either increase or decrease the benefits of this study?

If Yes, please explain: It'll increase the benefits of the study in that randomization into groups allows investigators to say that the educational intervention caused the learning (if learning occurs in the treatment group).

4. Do these changes either increase or decrease the risks or the risks of this study? If Yes, please explain and justify the increase in risk relative to the benefits: No, it does not increase risk to participants.

If the proposed changes require additional or changes to documents (such as the consent form), list these document titles.

One statement on the invitation to participate will change. I've also made formatting changes on the questionnaire and simulation observation instrument based on advice from a measurement consultant and based on new learning that occurred from a pilot test run that was recently completed. The script may also change slightly to adjust for changes. I spoke with [name] about the overall change in plans and I wasn't sure if IRB be needs to approve any and all changes (formatting and otherwise) to each document if the risks are not increasing or if minor changes to forms can be made without additional advance approval?

ST. CATHERINE UNIVERSITY REQUEST FOR APPROVAL FOR THE USE OF HUMAN SUBJECTS IN RESEARCH APPLICATION

IRB APPLICATION DOCUMENT CHECKLIST

The items listed below are the application, forms and supporting documents to be uploaded to Mentor IRB for your protocol/application submission. Consent forms and additional supporting documents may be uploaded to separately; see Mentor IRB Directions. For questions, contact the IRB Assistant at [contact] or [contact].

	IRB Application
	PI Documentation/CITI Training for Investigator(s)*
N/A	PI Documentation/CITI Training for Faculty Adviser (if applicable)*
	Informed consent form
N/A	Child assent form (if applicable)
	Recruiting materials (phone script, fliers, ads, etc)

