Internal consistency reliability of SDSC data will be collected during the training session. For this aspect of the study, a protocol will be issued to ensure consistent administration and scoring of the 26 idem assessment.

Data Analysis. Results of the training protocol and SDSC internal consistency reliability data will be analyzed. Data analysis of the feasibility of training protocol will be conducted using statistics for the numerical data and a systematic process of coding and theme identification for non-numerical data. Both within group and between group analyses will be conducted. Paired T-test statistics will be used to analyze changes that occur within groups pre-training vs. post-training, after calculating both total scores and sub scores of competence Likert scale ratings. Between group comparisons (comparing professional vs. non-professional) will be made using 2 sample T-test after calculating mean score change for each participant. Information provided by participants in response to open ended questions will be analyzed via a qualitative type coding process. Investigators will first code the data and analyze for themes independently and then discuss collectively. Any discrepancies will be resolved via discussion and

further examination of the data. Internal consistency reliability or how well test items measure the same construct, will be analyzed using Cronbach's Alpha.

d. Expectations of Participants: Give a step by step description of all procedures that you will have participants do. Attach any surveys, tests, instruments, interview questions, data collection forms, etc. that you will use with participants.

Participants will complete a baseline questionnaire to determine their level of knowledge or competence related to a select aspects of the NTPC intervention (i.e. state of the evidence, outcome measurement, sleep care positioning methods and equipment, & risk factor monitoring).

Participants will receive a 4-8 hour sleep care positioning training protocol. Participants will learn about various strategies used to implement NTPC and gain practice in assessments, positioning equipment and methods and development of risk monitoring plan. The content will be delivered primarily using electronic interactive tutorials and some in-person training. As a part of the training, participants will be asked to discuss and apply information relevant to their own child or client (if professional care provider).

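### Participants are randomised to training or handout, but no stated test compares the two arms; the only two-sample t-test is of caregiver type

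*Combined protocol and SAP*

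**What the plan says.** **Design.** Item 1 of the IRB Amendment Request Form (April 2018) states that "the participants will be randomized into treatment group (receives the sleep care positioning 2-hour online education program) and control group/lesser intervention" groups. Item 2 justifies this by the comparison group, which is expected to show more about the program "than would occur with only one pre/post group". Item 3 gives the benefit: investigators will be able to say that the education caused the learning, on condition that learning is seen in the treatment group.

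**Analysis.** Section 1.c, Data Analysis, opens with a general promise: "Both within group and between group analyses will be conducted". It then says what each kind is.
- Within groups: "Paired T-test statistics will be used to analyze changes that occur within groups pre-training vs. post-training", on total scores and sub scores of the competence ratings.
- Between groups: "Between group comparisons (comparing professional vs. non-professional) will be made using 2 sample T-test", on each participant's change.

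The rest of the section covers qualitative coding and Cronbach's alpha for the SDSC. The amendment's nearest approach to an analysis concerns the new quiz: "This information will be compared along with the results from the questionnaires and demonstration of positioning a person in the sleep system". It names no test, time point or arm contrast.

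**Timing.** Under amendment item 1, controls are told their group after the lesser intervention, "the post-questionnaire and the demonstration of sleep positioning with mock client". Then: "On the same day the control group will be given the option to complete the same educational package as the treatment group". Section 1.d describes two later questionnaires rather than one: post-training on the same day, and post-simulation up to two days afterwards.

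**The concern.** The amendment randomises in order to attribute learning to the education. Neither stated test can do that. A paired test shows that scores changed within a group; it does not show why. The professional versus non-professional test compares groups that were not formed by randomisation, so it does not use the randomisation at all.

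Self-rated competence can rise in both arms through a second pass at the same questionnaire, through expectancy, or through the web links in the handout. Item 3 of the amendment makes the causal statement depend on learning in the treatment group and does not mention a difference from control. Read together with the Data Analysis text, this leaves a direct route by which a gain common to both arms is reported as an effect of training.

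Timing is a secondary matter. If an arm contrast used the later post-simulation questionnaire, some controls could already have taken the optional training, and the contrast would shrink. The SDSC reliability aim is not affected.

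**Working it through.** **1. Is there a test by arm?** The documents state no power, effect size or significance level, so there is no figure to reproduce. The check is to set the design against the analysis.

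| Element | Where | Groups compared |
|---|---|---|
| Randomisation | Amendment, item 1 | Training vs handout |
| Paired t-test | 1.c Data Analysis | None (pre vs post within a group) |
| Two-sample t-test on change | 1.c Data Analysis | Professional vs non-professional |
| Quiz, questionnaire, demonstration | Amendment, item 1 | To be compared; groups and test not named |

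No row pairs a test with the randomised groups. The likely reason is that the application text was not updated: section 1.c, Description of training protocol, still gives the training to every participant.

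**2. What the paired test does when training adds nothing.** From the documents: total of 40 (section 1.c, Target Population). Assumed: 20 per arm, two-sided 5% level, no dropout, and the same true gain in both arms.

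For a gain of g SDs of change, the noncentrality is g × √n. With g = 0.5 and n = 20 it is 0.5 × √20 = 2.24, on 19 degrees of freedom. The probability of a significant result in the training arm is 0.56 (0.46 with 16 in the arm, 0.65 with 24). For other shared gains at n = 20:

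| Shared gain (SD of change) | Paired test significant in training arm |
|---|---|
| 0.3 | 0.25 |
| 0.5 | 0.56 |
| 0.8 | 0.92 |
| 1.0 | 0.99 |

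The test is right that change occurred within the arm, but that change is not a training effect.

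Setting two separate paired tests side by side does not solve this. At g = 0.5 the pattern of training significant and handout not significant has probability about 0.56 × (1 − 0.56) = 0.25 (0.24 in a simulation of 20,000 trials). In the same simulation a direct two-sample test between arms was significant in 5.1% of trials.

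**3. Precision of the missing contrast.** Take the score SD as 1 at baseline and post, with correlation ρ between them. The 95% CI half-widths are:
- t-test on change: t(0.975, 38) × √[2(1 − ρ)(1/n₁ + 1/n₂)]
- ANCOVA: t(0.975, 37) × √[(1 − ρ²)(1/n₁ + 1/n₂)]

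For example, 20/20 and ρ = 0.5 give 2.024 × √0.100 = 0.64 and 2.026 × √0.075 = 0.55.

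| Split | Method | ρ = 0.3 | ρ = 0.5 | ρ = 0.7 |
|---|---|---|---|---|
| 20/20 | t-test on change | 0.76 | 0.64 | 0.50 |
| 20/20 | ANCOVA | 0.61 | 0.55 | 0.46 |
| 16/24 | t-test on change | 0.77 | 0.65 | 0.51 |
| 16/24 | ANCOVA | 0.62 | 0.57 | 0.47 |

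With 20 per arm, the t-test on change has 34% power for a true arm difference of 0.5 SD of change and 69% for 0.8. It reaches 80% at about 0.91.

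**4. Dilution, only if a late questionnaire were used.** If a share f of controls answered after the optional training and had its full effect, the expected contrast is (1 − f) × the true effect: 75% of it at f = 0.25, and 50% at f = 0.5.

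**The case against.** The strongest reply is that this is unrevised text rather than a choice. The Data Analysis section was written for one group. The amendment plainly wants a comparison group and says results will be compared. The section already promises between-group analyses and supplies a two-sample t-test on change, so a sensible analyst would run it by arm. The study is about feasibility, and a formal efficacy test is not obligatory. The 0.56 is ordinary power of a paired test and misleads only someone who ignores the control arm. On timing, the paired test is specified as pre- versus post-training, and no stated test uses the late post-simulation form.

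Much of this is fair. The intent to compare is clear, the method is at hand, the numbers rest on assumed inputs, and the timing point is peripheral. The change-score t-test by arm would also be valid under randomisation, so ANCOVA is the more precise option, not the only one.

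The central point remains. The section defines its between-group comparison explicitly, and the definition is caregiver type. Feasibility status does not remove the need for an arm comparison when the amendment itself claims a causal conclusion and words it in terms of the treatment group alone. The data for the right analysis will exist, but the plan does not commit to that analysis.

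**Conclusion.** The concern holds, and the text should be corrected before the data are analysed. The comparison for which the design was changed has no specified analysis, and the only between-group test named is on a factor that was not randomised. That conclusion comes from the wording and needs no assumption.

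The size of the risk is illustrative. With 20 per arm and a shared gain of 0.5 SD of change, the training-arm paired test is significant a little more than half the time (0.56) although training adds nothing. A direct arm comparison holds that error near 5%. Arm sizes, correlation, SDs and the shared gain are all assumed.

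Two parts of the file and the attached questionnaires and observation instrument were not available. Whether the demonstration yields a score could therefore not be settled.

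**What to change.** Add to section 1.c, Data Analysis, wording to this effect:

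> The effect of training is the between-arm difference (training minus handout) in the total competence score from the post-questionnaire completed before controls are told their group and before any optional training. It is estimated by ANCOVA adjusting for the baseline score, with a 95% CI. Paired t-tests and the professional versus non-professional comparison are secondary or descriptive. Any causal statement rests on the between-arm difference.

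Naming the total score settles which score carries the contrast, since the section computes sub scores as well; these can be secondary. At minimum, apply the existing two-sample t-test on change to training versus handout.

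Compare the demonstration by arm if the observation instrument produces a score; section 1.c, Data Collection, describes structured notes against competence criteria and states none. Compare the quiz by arm only if controls take it before the optional training. Amendment item 1 does not list the quiz among what they complete before disclosure, so this may need a change to the order of events.

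The cost is a few sentences and no new questionnaire data. The reported effect may be smaller than the pre/post gain. The interval will be wide: a half-width of about 0.5 to 0.6 SD with ANCOVA, or 0.5 to 0.8 SD with the t-test on change, at 20 per arm and ρ from 0.3 to 0.7.

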Research Questions. This project investigates both the feasibility of a sleep care positioning training protocol and the internal consistency reliability of the sleep disturbance scale for children (SDSC), a 26 item Likert-type rating scale developed by Bruni et al. in 1996 to evaluate sleep disturbances via caregiver report. Two Population Intervention Comparison Outcomes (PICO) questions will be addressed: 1. Is the training protocol feasible for use in training caregivers? 2. Does SDSC applied to children with cerebral palsy (CP) in the United States have sufficient internal consistency reliability for use in intervention research? Question one includes the following sub questions: A. Do caregivers have perceived competence and capacity to position children with CP (or similar mobility limitations) for sleep using sleep care positioning systems? B. Does the training protocol prepare caregivers to implement nighttime postural care (NTPC)?

Target Population. A convenience sample of 40 adult participants identified as professional or non-professional care providers (primarily from two community organizations that specialize in serving clients with CP) will be recruited for the study. Care providers of children with severe CP (those with limited ability to move and/or whom require use of a wheelchair) aged 6 to 12 are the primary target population, since this matches the intended sample of the future intervention study. However caregivers of children whom are outside of the 6-12 age range whom are candidates for NTPC and have similar mobility limitations as those with severe CP will not be excluded. Professional care providers might be nurses, occupational and physical therapists, assistive technology providers, etc. Non-professional care providers may be family members, care attendants, etc. Only individuals with knowledge of the child's sleep habits or routines will be included in the study

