This is a feasibility study. Feasibility studies are completed in advance of larger studies to better determine study design and are thought to help investigators avoid undesirable consequences from occurring when embarking on the larger studies (NIHR, 2017; Thaban et al., 2010). To understand the training protocol feasibility, data will be gathered from participants via questionnaire pre-training and post-training and via observational notes at the time of intervention simulation. Quantitative methods will be used to analyze numerical data and qualitative type methodology will be used to examine subjective data; however, the primary methodology of this study is quantitative.

Description of training protocol. All participants will receive the sleep care positioning training protocol with content on NTPC intervention implementation strategies. The primary topic areas include state of the evidence, outcome measurement, risk factor monitoring, and sleep care positioning methods and equipment. The content will be delivered using primarily electronic interactive tutorials, however some hands-on training may take place in person. Total training time is anticipated to require between 4 and 8 hours. Participants will simulate aspects of the intervention (with mock client, either researcher or actor) at the end of the training session. Additionally participants will be given the option of demonstrating aspects of the intervention with their own child (or child for whom they provide care) after completion of the training session and simulation.

Data Collection. Data will be collected to assess both the training protocol and the SDSC internal consistency reliability. To assess feasibility of the training protocol, data will be collected at baseline, post-training and post-simulation via questionnaire. The questionnaires (developed by investigators) contain Likert type rating scales and semi-structured questions about both participants' perceived competence to implement aspects of intervention and perceptions of the training protocol efficacy. A simulation observation instrument (developed by investigators) contains a structured format by which investigators can document observational notes of caregiver performance at time of intervention simulation. For this aspect of the study, raters will be trained by investigators to document observations of participant caregiver performance based on a set of criteria of competence.

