a. Recruitment Method: Describe how you will recruit your subjects? Attach a copy of any advertisement, flyer, letter, or statement that you will use for recruitment purposes.

Care providers (both professional and non-professional) whom have previously identified having interest in nighttime postural care training sessions at St. Catherine University or whom have considered NTPC as an intervention for their children/clients will be recruited for participation in the study. Care providers from two organizations (Gillette Children's Specialty Healthcare and LiveLife Therapy Solutions, Inc.) have already verbalized having interest in participation and will be invited to participate. Additionally, individual care providers (professional) from other organizations known to have interest in the NTPC intervention will also be invited.

A flyer will be sent via email to recruit participants for the study. This flyer will be/is attached to the application. Additionally the following script will be included in the body of the email.

"Hello (name), [As you know], I'm conducting a research study entitled "Nighttime postural care: Caregiver training and outcome measure feasibility" at St. Catherine University. I/We am/are trying to determine whether a training program I/we developed will be useful in preparing care providers (both non-professional and professional) to position and monitor children with cerebral palsy or movement limitations for sleep using sleep care positioning systems. I hope that you can participate by attending my/our sleep care positioning training session and completing a questionnaire rating the training. By participating in this research study you will attend a 4-8 hour training session and gain learning in a new sleep-based positioning intervention. You will also receive \$50/75 gift card and continuing education contact hours (if preferred by professional care providers). The gift card is being funded by St. Catherine University APDC grant # 00-1471-1.

"Also, if you are a professional care provider and know of any non-professional care providers (i.e. family member, care attendant, etc. of child with cerebral palsy whom might be a candidate for sleep-based positioning interventions) whom might be interested in participating in this study, please send their contact information (via encrypted email if verbal permission is given) to [name]"

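### The professional versus non-professional comparison of raw change has no arm term since the handout arm was added, and its result could be distorted if one caregiver type starts near the top of the scale

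*Combined protocol and SAP*

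**What the plan says.** The competence measure is described in section 1c of the IRB application, under Data Collection: "The questionnaires (developed by investigators) contain Likert type rating scales". The number of items and the scoring range are not given. Under Data Analysis, scores are analysed "after calculating both total scores and sub scores of competence Likert scale ratings", and the only between-group test named is: "Between group comparisons (comparing professional vs. non-professional) will be made using 2 sample T-test after calculating mean score change for each participant". It has no baseline term, no check for scores at the maximum and no reference to study arm.

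That section belongs to a design in which everybody was trained. The Amendment Request Form, item 1, changes this: "the participants will be randomized into treatment group (receives the sleep care positioning 2-hour online education program") or to "control group/lesser intervention (handout with series of web links) groups". The amendment says that quiz, questionnaire and demonstration results will be compared. It names no test and does not revisit the caregiver-type comparison. Neither the allocation ratio nor stratification by caregiver type is stated.

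The sample is "A convenience sample of 40 adult participants identified as professional or non-professional care providers" (section 1c, Target Population), with no planned split between the types. A baseline rating will be available: "Participants will complete a baseline questionnaire to determine their level of knowledge or competence" (section 1d).

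**The concern.** There are two separate problems.

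The first is arm. Once half the sample, say, receives only a handout, the change score averaged within a caregiver type depends on how many of that type were trained. A difference between types can then partly be a difference in arm mix, and it is no longer a statement about the programme.

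The second is the ceiling. Caregiver type is not randomised, and a bounded rating leaves less room to rise for whoever starts higher. Much of the training content overlaps the work of therapists and equipment providers, so a head start for professionals is a reasonable expectation, though the documents do not state one. If they start close to the maximum, the same true learning gives a smaller observed change.

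At stake is how one comparison in a feasibility study is read: a difference could be credited to caregiver type when it comes from arm mix or from the scale.

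**Working it through.** The plan has no figure to reproduce: the 40 is a convenience sample without a power calculation.

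**Inputs from the documents.** 40 participants, two caregiver types, two randomised arms, a two-sample t-test on change in a Likert rating.

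**Assumed inputs.** 20 professionals and 20 non-professionals; 1:1 unstratified allocation; 12 items scored 1-5, rounded and clipped; between-person SD 0.6; item SD 0.6; true gain 1.5 with the programme and 0.3 with the handout, identical for both types; non-professional start 2.5.

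**Step 1: effect of arm mix.** If both types learn equally and there is no ceiling, the expected difference in change is (share of professionals trained - share of non-professionals trained) x (programme gain - handout gain). With 12/20 and 8/20 trained: (0.6 - 0.4) x (1.5 - 0.3) = 0.24 in favour of professionals. With the shares reversed it is 0.24 against them.

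**Step 2: how large chance imbalance is.** The number of professionals in a programme arm of 20 drawn from 40 has variance 20 x 0.5 x 0.5 x 20/39 = 2.56, so SD 1.60. Each extra professional displaces a non-professional, so the difference in shares has SD 2 x 1.60/20 = 0.16. The chance that the shares differ by at least 20 points, in either direction, is 34%. The contribution to the contrast has SD 0.16 x 1.2 = 0.19. The remaining noise has SD about 0.09, and sqrt(0.19² + 0.09²) = 0.21, in line with the simulated value of about 0.20. Accounting for arm leaves about 0.09. The imbalance centres on zero. In a second simulation, the planned test kept about 5% false positives when there was no head start, so ignoring arm costs precision, not validity on average.

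**Step 3: ceiling.** With equal true gains, the difference in observed change (professional minus non-professional) is:

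| Professional start | Arms pooled, 20 per type | Rejections | Programme arm alone |
|---|---|---|---|
| 3.0 | about -0.04 | about 5% | -0.07 |
| 3.5 | about -0.14 | 11% | -0.26 |
| 4.0 | about -0.28 | 33% | -0.53 |

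The pooled artefact is about half the programme-arm one, because handout participants gain little and rarely reach the maximum.

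The second simulation (10 items, item SD 0.7, SD of gain 0.3, gains 1.5 and 0.5, arms pooled) shows the dependence on room at the top, for head starts of 0.5, 1.0 and 1.5:
- Non-professional start 1.5: +0.07, +0.07, +0.03.
- Non-professional start 2.5: -0.04, -0.16, -0.31.
- Non-professional start 3.0: -0.12, -0.27, -0.47 (rejections 10%, 34%, 80%).

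**Step 4: what each remedy does.**
- *An arm term* removes the noise in step 2 but not the shift in step 3. Taking 0.09 as the residual SD, a shift of -0.14 goes from 0.14/0.20 = 0.7 SD to 0.14/0.09 = 1.6 SD. The artefact becomes easier to detect, so the arm term needs the ceiling reporting beside it.
- *Testing post-training ratings alone* carries the head start into the result: in an all-trained sample with a professional start of 3.5, professionals finish 0.72 higher although gains are equal.
- *Baseline adjustment* (with an arm term, second simulation) turns -0.27 into +0.08 at start 3.0 with head start 1.0. At start 2.0 with head start 1.5 it turns -0.15 into +0.20, with 15% rejections. It can over-correct and is not sufficient alone.

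**Step 5: precision** (two-sided 5%, 80% power). All 40: (1.96 + 0.84) x sqrt(1/20 + 1/20) = 0.89 SD. Programme arm only, 10 per type: 2.80 x sqrt(1/10 + 1/10) = 1.25 SD.

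**The case against.** A reader might infer that professionals will look as if they benefit less, and that pooling the arms is the reason. The documents do not support this. They give no baseline levels and no scale range. Section 3a recruits people "whom have previously identified having interest in nighttime postural care training sessions at St. Catherine University or whom have considered NTPC", and applies this to both caregiver types, so it does not separate them. If both start low, there is little or no deficit (step 3). Pooling does not produce the ceiling artefact; it dilutes it, and chance arm imbalance is as likely to favour professionals as not.

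A reader might also attach much higher rejection rates to the plan. Rates of about 37% and 89% (professional starts 3.5 and 4.0) arise only if all participants are trained, with 10 per type. The pooled plan gives 11% and 33%.

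Two further defences have force. Pooling is not a stated rule; it follows from a section that was not updated when the design changed. And nothing in the documents says that this comparison will decide whom a later study trains; the research sub-questions concern caregivers generally.

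What stands is narrower: the only between-group test named ignores arm in a design that now has two, and it uses raw change on a bounded scale between groups that were not randomised.

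**Conclusion.** The point holds as a low-cost improvement, not as a demonstrated bias. Two parts rest on the text: no arm term or restriction was added with the handout arm, and the comparison uses unadjusted change in a bounded rating.

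The sizes rest on assumptions. Ignoring arm roughly doubles the SD of the contrast (0.20 against 0.09) with 20 per type and gains of 1.5 and 0.3; a smaller difference between the arm gains would shrink this. The ceiling artefact runs from negligible to about -0.28 points pooled and -0.53 in the programme arm over the professional starts examined. It requires both a head start and scores near the maximum, and the documents establish neither.

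**What to change.** - Randomise separately within professionals and non-professionals; caregiver type is known beforehand. Keep arm in the analysis as well: with balanced arms, a t-test that ignores arm would overstate the standard error.
- Restate the caregiver-type comparison for the amended design, either by arm or with an arm term, and show the programme-arm result separately.
- Beside the change, report baseline and post-training ratings and the percentage at the top category, by caregiver type.
- State in advance that a smaller change from a high baseline is not evidence of less benefit.
- Do not replace the change comparison with a test of post-training ratings alone.

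The cost is two randomisation lists instead of one, a short rewording and a little more analysis. The programme-arm-only estimate will be less precise (detectable difference about 1.25 SD against 0.89 SD, assuming equal splits) and should be presented as descriptive.
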